7.3 OPERATING PROCEDURES FOR SPECIMEN COLLECTION

Peripheral blood and bone marrow specimen collection will be performed as delineated in the Table 1 Schedule of Assessment Section 4.3 and additionally at the times when peripheral blood and bone marrow collections are performed for clinical care such as GVHD, toxicity and/or disease relapse.

Bone marrow: 4 x 8mL will be collected in green top sodium heparin tubes (~20-30 mL). Re-adjustment of the direction of bone marrow aspirate needle should take a place after each 10 cc is collected to prevent hemodilution. At the time of collection, green top tubes must be thoroughly mixed to prevent clotting.

Peripheral blood: 5x8mL green top sodium heparin tubes of blood (~40mLs) will be collected at each time point.

Specimens should be labeled with the patient's study number (given at the time of registration), study number, sample collection date and time, and sample source (PB or BM). Sample collection date and time, and sample source (PB or BM) will be recorded on correlative collection worksheet and copy included with delivery. All data should be kept in laboratory log. At each sampling time, BM and PB mononuclear cells (PBMC) will be processed via Ficoll density gradient centrifugation. The washed cells will be counted, triaged for DNA isolation, and viably cryopreserved using a controlled-rate freezer with transfer to the vapor phase of liquid nitrogen for long-term storage ([name] laboratory).

The Sidney Kimmel Comprehensive Cancer Center (SKCCC) specimens should be delivered to the [name] laboratory immediately after collection.

[figure not shown]
Specimen collection / processing: PB and BM specimens should be collected as outlined in the Trial Flow Chart 6.0.

7.3 FREEZING PROTOCOL (SOP)

1. Prepare 50mL falcon tubes with Ficoll density grade media (Histopaque)
 - Ratio Ficoll : blood should be 1:1
 - Do not exceed 20mL Ficoll to 20mL blood (i.e. total volume of 40mL)
2. Slowly layer blood on top of Ficoll
 - Use whole blood or marrow aspirate, do not dilute with PBS or anything else
 - Be careful not to mix the two layers

3. Centrifuge: spin at the following settings:

- 1240rpm (=364G)
- 20 Celsius
- Break off
- 30min

4. Prepare 6 small Eppendorf tubes
 - Take off 6 x 500ul of plasma (top layer; blood only; not for BM aspirate) and put it into Eppendorf tubes
 - Be careful not to get into any layer but the plasma layer
 - Long term storage in -80 Celsius freezer
5. Soak up PBMC layer with transferring pipette and put it into a new 50mL Falcon tube
 - Fill up with PBS up to 45mL, vortex
 - Centrifuge: Spin at 1240 rpm (=364G), 4 Celsius, break high, for 5 minutes
6. First wash

- Dump supernatant
- In case of visible RBC contamination add 1ml of lysing buffer to the cell pellet, vortex, and leave for 1 minute. Then add 20mL of PBS
- If there is no RBC contamination only add 20mL of PBS and vortex
- Centrifuge: Spin at 1240 rpm (=364G), 4 Celsius, break high, for 5 minutes

7. Second wash

- Dump supernatant
- just add 20mL of PBS and vortex
- Centrifuge: Spin at 1240 rpm (=364G), 4 Celsius, break high, for 5 minutes

8. Count cells

- Dump supernatant
- add 1mL of PBS and vortex thoroughly
- take 10ul out and mix with 90ul of trypan blue
- count in hemacytometer

Study # _____
Pt ID# _____
Timepoint: _____
Cell count: _____
Date(time): _____

Blood or Marrow

9. Prepare freezing tubes and media

- Put cells in the meantime on ice
- Freezing media: FBS containing 10% DMSO
- 1.8mL vials labeled with study #, time point, cell count, date, type of specimen,

10. Final spin

- Add 20ml of PBS to the cells, vortex
- Centrifuge: Spin at 1240 rpm (=364G), 4°C, break high, for 5 minutes

11. Freeze cells - General rules

- PBMCs: 1.5mL freezing media per 10 million cells (=1 vial)
- BMNCs: 1.5mL freezing media per 30 million cells (=1 vial)

12. Freezing

- Put vials into [name]® (container with Ethanol, that gradually cools down samples) and put into -80 Celsius fridge for about 24 hours
- After 24 hrs (up to 48hrs) transfer vials into liquid nitrogen tanks (to minimize temperature fluctuations make sure you transport them there on dry ice)

Considerations regarding freezing and shipping

- Samples should optimally be processed the same day
- If there is a sample coming in late, keep it in the fridge (in 4°C) overnight and process them early the next morning.

- Samples processed should be stored in -80 Celsius for 24-48 hours and get transferred into liquid nitrogen thereafter
- If there are no liquid nitrogen tanks available, it's permissible to keep samples in -80 Celsius for up to 2 weeks, but no longer.

Important considerations:

1. All work should be done using standard BSL2 procedures (blood and body fluid precautions).
2. Maintain a clean workspace and use a containment laminar airflow hood when possible.
3. Minimize the chance of contamination.
4. Work quickly but methodically.
5. Keep tubes closed as much as possible and work quickly.
6. Change gloves frequently and maintain situational awareness

8. RISKS

8.1. IDELALISIB RISKS

Known toxicities of idelalisib: idelalisib is FDA approved for the treatment of relapsed chronic lymphocytic leukemia/small lymphocytic lymphoma and follicular B-cell non-Hodgkin lymphoma.

Idelalisib may cause:

1. ALT/AST elevations and hyperbilirubinemia (most frequently occurs within the first 12 weeks of treatment); incidence of serious hepatotoxicity: 14.0%
2. Diarrhea (mean time to occurrence 7.2 months); incidence of serious/severe diarrhea: 14.0%
3. Pneumonitis; incidence <5%
4. Neutropenia: Grade 3 or 4 neutropenia occurs in approximately 31% of patients receiving the 150mg bid dose.
5. CYP3A affects: CYP3A inducers can reduce the AUC of idelalisib by 75%; CYP3A inhibitors can increase the AUC of idelalisib by 1.8 fold; idelalisib is strong CYP3A inhibitor.
6. Increase risk of developing PCP
7. CMV viremia

8.2. RISK MINIMIZATION

Patients will have comprehensive metabolic panels performed every 14 days through day +180 , then monthly through day +270.

Patients undergoing allo BMT may develop intestinal aGVHD which may present with diarrhea or ileus. All patients with >3 grade diarrhea will also be evaluated for aGVHD in addition to idelalisib dose modification.

Patients undergoing allo BMT often develop late neutropenia after achieving neutrophil recovery. To help limit the depth of neutropenia that could be attributable idelalisib, idelalisib will be dosed at 100mg bid, the

suggested dose reduction for patients experiencing an ANC $<.5\text{Gi/L}$ while on the standard 150mg bid dosing schedule

CYP3A interactions. Commonly, patients undergoing allo BMT require azole based antifungal prophylaxis and/or treatment. Patients receiving posaconazole or voriconazole will have these levels checked every 14 days while receiving idelalisib.

In the post allo BMT patient population, novel toxicities need to be considered: Non T-cell engraftment and acute GVHD. Stopping rules, as defined in section 6.0 will be followed to stop this study, if compared to placebo I controls, the differential in incidence of toxicities of any kind between the idelalisib group and the placebo control group is $>10\%$.

CMV viremia: CMV serum PCR analysis every 14 days between days 90-and day +120, then monthly through day +270: treat according to BMT policy guidelines.

PCP: continue BMT policy guidelines of PCP primary prophylaxis for at least through the time of active-study participation.

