4. STUDY PROCEDURES

- Idelalisib, 100mg twice daily, starting day +90 (+/- 10 days) and at least five days after the discontinuation of filgrastim, if ANC greater than 1000 and PLT $50 > \text{Gi/L}$ and continued through day +270. Patients will have a CBC with platelet count and comprehensive metabolic panels performed every 14 days beginning at day +90 through day +120, then monthly through day +270.

Patients will be monitored for treatment-limiting toxicities defined as Idelalisib interruption for >14 days, or any other Grade 3 or higher adverse events as defined by CTCAE IV not captured in the protocol for dose de-escalation. All Adverse events will be collected and assessed for causality but only AEs Grade 2 and higher will be recorded on the Master AE log. Patient's idelalisib will be dose adjusted for the expected toxicities of idelalisib including pneumonitis, hepatitis, neutropenia, thrombocytopenia and loose stools.

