4.3. TABLE 1. SCHEDULE OF ASSESSMENTS

	Screening and Baseline ()	Cycle 1, Day 1 Day +90 (± 10 Days)) Cycle 1, Day 15	(± 7 Days) Cycles 2-6, Day 1	30 days Post last dose	Month 12 (± 14 Days)
Informed Consent ^a	Days 60 -100					
Medical History	X					
Physical Exam	X	X		X	X	X
AE Assessment	X	X		X	X	X
CBC with diff	X	X	X	X	X	X
Comprehensive metabolic panel e (CMP) ^b	X ^b	X ^b	X ^b	X ^b	X ^b	X ^b
PT, PTT, INR	X					
Serum β -HCG (if applicable)	X					
CMV PCR ^d	X ^d	X	X	X		
Dispense Idelalisib		X		X		
Standard of care per institution						
T-cell chimerism	X					X
Bone marrow biopsy (as std of care)	X					X
aGVHD/cGVHD assessments	X	X	X	X		X
Correlative studies ^c	X	X		X ^c		X

^aInformed consent will be collected beginning on Day +60 after BMT until Day +100.

^b CMP to include BUN, creatinine, sodium, potassium, chloride, AST, ALT, total bilirubin, alkaline phosphatase.

^c Additionally specimens should be obtained from peripheral blood and bone marrow collections as a part of routine clinical care such as GVHD, toxicity and/or disease relapse Correlative peripheral blood samples should be collected on Day 1 of every other cycle beginning with Cycle 2

^d Cytomegalovirus (CMV) viral load assay will be monitored by PCR every 14 days between days +90-and day +120, then monthly through day +270: treat according to BMT policy guidelines.

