5. KNOWN TOXICITIES AND DOSE ADJUSTMENTS

5.1. KNOWN TOXICITIES OF IDELALISIB

Idelalisib is FDA approved for the treatment of relapsed chronic lymphocytic leukemia/small lymphocytic lymphoma and follicular B-cell non-Hodgkin lymphoma. Idelalisib may cause:

- ALT/AST elevations and hyperbilirubinemia (most frequently occurs within the first 12 weeks of treatment); incidence of serious hepatotoxicity: 14.0%
- Diarrhea (mean time to occurrence 7.2 months); incidence of serious/severe diarrhea: 14.0%
- Pneumonitis; incidence <5%
- Neutropenia: Grade 3 or 4 neutropenia occurs in approximately 31% of patients receiving the 150mg bid dose.
- Rash: Grade 3 or 4 rash occurred in approximately 21% of patients receiving the 150mg BID dose.
 - CYP3A affects: CYP3A inducers can reduce the AUC of idelalisib by 75%; CYP3A inhibitors can increase the AUC of idelalisib by 1.8 fold; idelalisib is strong CYP3A inhibitor. A list of these drugs can be found in appendix 4. Importantly, with direct relevance to this study is the lack of data supporting strong interaction with voriconazole. Azoles are often the medication of choice for patients with suspect fungal or anti-bacterial non-responsive fevers during alloBMT. The elimination of idelalisib is predominantly mediated by the hepatic pathway. Idelalisib is primarily metabolized by aldehyde oxidase with a lesser involvement of cytochrome P450. The major metabolite of idelalisib is GS-563117. Data indicate that CYP3A inhibition by concurrent use of azoles may result in modestly higher exposures of idelalisib, but the change is not of clinical relevance²¹. In this study, as the dosing of idelalisib is already reduced to 100mg bid to provide additional risk mitigation. Additionally, patient's receiving azole therapy while on idelalisib will have serum levels monitored to adjust to target levels.

Therefore, to protect patients in this study the following measures are employed:

- Patients will have comprehensive metabolic panels performed every 2 weeks through day +120, then monthly through day +270.
- Patients post alloBMT may develop intestinal aGVHD which may present with diarrhea or ileus. All patients with ≥ 3 grade diarrhea will also be evaluated for aGVHD in addition to idelalisib dose modification.
- Patients post alloBMT may develop aGVHD which often presents with a generalized cutaneous rash. All patients with ≥ 3 grade rash will also be evaluated for aGVHD in addition to potential idelalisib dose modification.

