Transaminitis and hyperbilirubinemia can occur with idelalisib use and are also common in allogeneic bone marrow transplant recipients. For patients experiencing an AST/ALT or bilirubin >5x ULN that is unexplained by other factors, hold study drug until the parameter is \leq 2ULN and restart at 100mg once daily. If the parameter should rise again >5 ULN, discontinue study drug. For AST/ALT >20x ULN (or Bilirubin >10x ULN), regardless of attribution, study drug should be permanently stopped.

DIARRHEA

Diarrhea can occur with idelalisib use and is also common in allogeneic bone marrow transplant recipients. Prior to major pharmacologic intervention, common infectious causes of loose stooling should be evaluated. For loose stools, in the absence of major infections, anti-motility agents may be offered and/or light steroid preparations. For patients with significant stooling, >1L daily, hold study drug and consider colonic biopsy if there is evidence to suggest aGVHD. Once stooling is <0.5L day, restart at 100mg oncedaily. If stooling should

again increase to >1L daily, discontinue study drug. For life-threatening diarrhea, study drug should be permanently stopped.

NEUTROPENIA AND THROMBOCYTOPENIA

Neutropenia and thrombocytopenia can occur with idelalisib use and are also common in allogeneic bone marrow transplant recipients. For ANC < 500 or PLT < 25,000, monitor CBC with differential weekly, hold study drug until ANC >1,000 and PLT count >50,000 and restart at the original dose. If a subject develops ANC < 500 or PLT < 25,000 a second time, hold study drug until ANC >1,000 and PLT count >50,000 and restart at 100mg once daily. If a subject who is on 100mg once daily develops ANC < 500 or PLT < 25,000, discontinue study drug.

Acute GVHD: Patients with symptomatic aGVHD will be treated as per institutional guidelines. If after seven days of therapy there is evidence of progressive aGVHD, study drug will be stopped for at least seven days. If it is determined that study drug was not causative of the aGVHD it may be restarted at the discretion of the primary oncologist. If after 14 days of active therapy there is no improvement of the aGVHD, study drug will be stopped for at least seven days. If it is determined that study drug was not causative of the aGVHD persistence it may be restarted at the discretion of the primary oncologist.

LATE ONSET NEUTROPENIA (LON)

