Appendix 2: Study Calendar and Schema

12.1. STUDY CALENDAR

	Screening and Baseline ()	Cycle 1, Day 1 Day +90 (± 10 Days)	Cycle 1, Day 15	Cycles 2-6 Day 1 (+/- 7 days)	30 days Post last dose	Month 12 (± 14 Days)
Informed Consent ^a	Days 60 -100					
Medical History	X					
Physical Exam	X	X		X	X	X
AE Assessment	X	X		X	X	X
CBC with diff	X	X	X	X	X	X
Comprehensive metabolic panel e (CMP) ^b	X ^b	X ^b	X ^b	X ^b	X ^b	X ^b
PT, PTT, INR	X					
Serum β-HCG (if applicable)	X					
CMV PCR ^d	X ^d	X	X	X		
Idelalisib		X		X		
Standard of care per institution						
T-cell chimerism	X					X
Bone marrow biopsy (as std of care)	X					X
aGVHD/cGVHD assessments	X	X	X	X		X
Correlative studies ^c	X	X		X ^c		X

^aInformed consent will be collected beginning on Day +60 after BMT until Day +100.

^bCMP to include BUN, creatinine, sodium, potassium, chloride, AST, ALT, total bilirubin, alkaline phosphatase.

^c Additionally specimens should be obtained from peripheral blood and bone marrow collections as a part of routine clinical care such as GVHD, toxicity and/or disease relapse Correlative peripheral blood samples should be collected on Day 1 of every other cycle beginning with Cycle 2

^dCytomegalovirus (CMV) viral load assay will be monitored by PCR every 14 days between days +90-and day +120, then monthly through day +270: treat according to BMT policy guidelines.

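### Section 8.2 runs 14-day metabolic panels to day +180, but sections 4 and 5.1 stop them at day +120, and the disputed days are over half of the stated 12-week liver-risk window

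*Combined protocol and SAP*

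**What the plan says.** The combined protocol and SAP states the frequency of the comprehensive metabolic panel (CMP) in five places.

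- Section 8.2: "comprehensive metabolic panels performed every 14 days through day +180", then monthly to day +270.
- Section 4: "comprehensive metabolic panels performed every 14 days beginning at day +90 through day +120, then monthly through day +270".
- Section 5.1, among the measures to protect patients: "comprehensive metabolic panels performed every 2 weeks through day +120, then monthly through day +270".
- Section 4.3 and Appendix 2 (12.1): a CMP at Cycle 1 Day 1, at Cycle 1 Day 15, and then under the column "Cycles 2-6, Day 1". No mid-cycle visit exists after Cycle 1.

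A footnote to both calendars puts AST, ALT, total bilirubin and alkaline phosphatase in the CMP, so it is the scheduled liver test. Section 8.1, repeating section 5.1, describes the risk as "ALT/AST elevations and hyperbilirubinemia (most frequently occurs within the first 12 weeks of treatment); incidence of serious hepatotoxicity: 14.0" per cent. Section 5.2 acts on the results: "For patients experiencing an AST/ALT or bilirubin >5x ULN that is unexplained by other factors, hold study drug until the parameter is" at or below twice the upper limit of normal.

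**The concern.** Both rules are in current text and they cannot both be followed after day +120. No section ranks one above the other. Section 4 and the two calendars are what staff would most naturally work from, so the likely outcome is the sparser schedule, with section 8.2 describing closer liver monitoring than patients receive.

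The disputed days matter because they lie inside the 12 weeks that the protocol itself names as the time when liver toxicity is most frequent. The hold and stop rules of section 5.2 can act on a laboratory abnormality only once a panel has been drawn. The primary goal of the trial is safety, so the monitoring schedule for a named toxicity should have one reading.

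**Working it through.** **Inputs.** Start on day +90, permitted range +80 to +100 (section 4). Risk window of 12 weeks = 84 days (sections 5.1 and 8.1). Last day of 14-day panels: +180 (section 8.2) or +120 (sections 4 and 5.1). The protocol defines neither a month nor a cycle length, so I take 28 and 30 days as the range. Six cycles over days 90 to 270 would suggest 30, but this is not stated.

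**Do the calendars take a side?** They do not print day +120 for the CMP; there it appears only in the CMV footnote. For a day +90 start, however, Cycle 2 Day 1 falls on day 118 (28-day cycle) or day 120 (30-day cycle), and every later panel is a full cycle apart. That is the day +120 pattern.

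**Share of the risk window in dispute.**
- Start day 90: window ends on day 174; (174 − 120)/84 = 54/84 = 64%.
- Start day 80: window ends on day 164; (164 − 120)/84 = 44/84 = 52%.
- Start day 100: window ends on day 184, but section 8.2 leaves 14-day panels at day 180; (180 − 120)/84 = 60/84 = 71%.

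Days 90 to 120 are monitored alike under both rules.

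**Panels and waits in days 121 to 174, day +90 start.** Assume that an abnormality is equally likely to begin at any time in the 54 days. A stretch that begins w1 days and ends w2 days before the next panel contributes (w1² − w2²)/2 to the total wait; the total is divided by 54.

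| Rule | Panels in days 121–174 | Mean wait (days) | Longest wait (days) |
|---|---|---|---|
| Section 8.2 | 132, 146, 160, 174 (4) | (12²/2 + 3 × 14²/2)/54 = 366/54 = 6.8 | 14 |
| To day +120, then every 28 days from day 118 | 146, 174 (2) | (26²/2 + 28²/2)/54 = 730/54 = 13.5 | 28 |
| To day +120, then every 30 days from day 118 | 148; next is 178 (1) | (28²/2 + (30² − 4²)/2)/54 = 834/54 = 15.4 | 30 |
| To day +120, then every 30 days from day 120 | 150; next is 180 (1) | (30²/2 + (30² − 6²)/2)/54 = 882/54 = 16.3 | 30 |

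Over the whole 84-day window, counting the day +90 panel, section 8.2 gives 7 panels and the day +120 rule gives 4 or 5.

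**Does day +180 cover the window?** It does for starts up to day 180 − 84 = +96. For a day +100 start the window runs to day +184, slightly past it.

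**The case against.** The strongest reply is that day +180 is simply a drafting slip. Two sections and both calendars fit day +120, section 8.2 largely repeats the list in section 5.1, and its CMV line uses the shorter rule: "CMV serum PCR analysis every 14 days between days 90-and day +120, then monthly through day +270". On that reading one number needs correcting and no patient loses anything that was intended. This stands as a possibility. The CMV line can also be read the other way, since it shows that section 8.2 gave the CMP a different end day from another test in the same section. The documents do not settle it. A reader might infer that the operative schedule breaks a deliberate commitment; the text does not show that +180 was deliberate.

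A second reply is that no clinical or statistical consequence is shown. That also stands. The protocol does not say where in the 12 weeks the liver risk falls, so the number of events in the disputed days is unknown. Both arms of this double-blind trial share one schedule. A reader might infer a distorted treatment-limiting toxicity rate or a bias between arms; nothing in the documents supports either.

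A third tempting inference is that hepatic holds would run past the 14-day interruption criterion merely because the next panel is a month away. Section 5.2 sets a weekly CBC for cytopenia holds and no interval for hepatic holds. But section 9.3.1 already calls for a clinically significant abnormal test to be repeated, and nothing ties that recheck to the scheduled panels. The missing interval is a detail to clarify and is not part of this point.

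**Conclusion.** The inconsistency is real and should be resolved, because the choice of end day changes how closely the liver is watched during most of the protocol's own risk window. For a day +90 start, days 121 to 174 would get 1 or 2 scheduled panels instead of 4, and the mean wait to the next panel roughly doubles, from 6.8 days to between 13.5 and 16.3.

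The end days and the 12-week window are the protocol's own. The panel counts also rest on a month or cycle of 28 to 30 days, and the mean waits on uniform onset within the disputed days. Unscheduled blood tests are not counted, because the protocol does not require them at any stated interval. The point concerns scheduled monitoring only.

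**What to change.** State one rule in sections 4, 4.3, 5.1, 8.2 and Appendix 2. The preferred rule is a CMP about every 14 days through day +180, then monthly to day +270, because it covers most or all of the 12-week window for every permitted start day. Setting section 8.2 to day +120 would also remove the contradiction at no cost, but it would leave over half of the window on monthly panels; if the sponsor chooses that, the reason should be given.

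In both calendars, add a Day 15 CMP to Cycles 2 and 3. With 28-day cycles and a day +90 start this gives days 118, 132, 146, 160 and 174, which match section 8.2 exactly. With 30-day cycles it gives days 120, 134, 150, 164 and 180: a mean wait of (14²/2 + 16²/2 + 14²/2 + (16² − 6²)/2)/54 = 434/54 = 8.0 days and a longest wait of 16. Writing the rule as Day 1 and Day 15 of Cycles 1 to 3 keeps text and calendar in step. Defining the cycle length would remove the remaining ambiguity.

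The cost is a short protocol clarification and 2 extra routine panels per patient (2 × 45 = 90 for the 45 patients in section 6). Counted strictly every 14 days, with monthly panels restarting at day 180, it is up to 11 − 8 = 3 per patient (3 × 45 = 135). A weekly CMP during hepatic holds, in parallel with the weekly CBC rule in section 5.2, would be a sensible optional addition.
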